### 2. Statistical methods

### 2.1. Data analysis general information

The final analysis will be performed by Qualitas Health personnel. IBM SPSS Statistics Version 29.0.0.0 (241) statistical software will be used to perform all data analyses and to generate tables, figures, and listings.

## 4-Mar-2022

### 2.2. Data included in the analysis

The study data will be analyzed and reported based on all patient's data when all participants have completed at least 2 tests or discontinued the study (ITT population).

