Along with the fist supplement order shipped to the new subscriptions, participants will receive the baseline hearth health test kit from ImawareTM. Participants will be contacted 3 and 6 months after and they will be sent subsequent kits once the confirmed adherence to the supplement. The test kits will monitor blood lipid levels across a supplementation period (baseline, month 3 and month 6) thanks to a finger prick blood drawing system. The age, height, weight, gender, fasting total cholesterol, LDL-cholesterol, HDL-cholesterol, calculated VLDL-cholesterol, triglycerides, as well as hs-CRP inflammatory marker, and glucose and HbA1c as diabetes indicator of each participant will be recorded over the study period. **Qualitas Health** will receive the aggregated data of the participants only for statistical analyses at their headquarter in Houston and store it in the company share drive with access restricted to those involved in the study. There will be no cost incurred for this analytical assessment to the participant.

Results for the per intended-to-treat (ITT) population will be first tested for normality before any other test will be conducted and baseline data was compared against month 3 and month 6 data. Based on the distribution of data, either Welch two-sample unequal variance t-tests or Wilcoxon Ranks sum tests will be used to compare two-tailed differences between groups. Differences will be considered statistically significant at a p value < 0.05, but the thresholds for the significance of the 20 clinical outcomes were adjusted for multiple variables by the Bonferroni adjustment method which decrease the significance of p-value from <0.05, down to <0.0025. Intervention

effect will also test using an analysis of covariance model (ANCOVA) adjusting for baseline parameters.

[figure not shown]

Figure 1-1 Study design

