### 1.1. Study objectives and endpoints

4-Mar-2022

The aim of this study is to assess the effectiveness of Almega®PL on improving blood markers associated with heart health of iwi customers. Specifically, we would like to confirm the decrease in cholesterol observed in our previous trial (Rao et al., 2020) while assessing the capacity to also decrease triglycerides (primary outcome). As a secondary objective we would like to understand if EPA, precursor of signalling molecules involved in the inflammatory response, could help decrease the inflammatory marker hs-CRP.

Objectives and related endpoints are described in Table 1-1 below

Table 1.1-1. Objectives and relative endpoint

| OBJECTIVES   | ENDPOINTS   | JUSTIFICATION FOR ENDPOINTS   |
|--|---|---|
| Primary  |   |   |
| Can Almega® PL
supplement decrease
triacylglycerides in a
generally healthy
population?  | Triglyceride change from baseline over 6-month period.  | Triglyceride levels is an
atherogenic lipid and an
important risk factor in
cardiovascular disease   |
| Secondary  |   |   |
| Can Almega® PL supplement replicate the decrease in VLDL and total cholesterol we observed in our previous clinical trial (Rao et al., 2020)? Will the results from a controlled population translate to the iwi costumers? Can Almega® PL | Total Cholesterol change from baseline over 6-month period. VLDL-Cholesterol change from baseline over 6-month period. LDL-Cholesterol change from baseline over 6-month period. HDL-Cholesterol change from baseline over 6-month period. hs-CRP change from baseline over 6-month period. Fasting glucose change from baseline over 6-month period. HbA1c change from baseline over 6-month period. | Cholesterol in plasma levels is atherogenic and a risk factor in cardiovascular disease. Hs-CRP is an age-related inflammatory market. Omega-3 help regulate the inflammatory response. |

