### Confidential

4-Mar-2022

|                      | Trial end interview | 
 
Participants exit email or phone interview
to address adherence.
 
   |
|----------------------|---------------------|--|
| End-Study
Month 3 |                     |  |
| Post-Study           | N/A                 | 
 
Data verification and statistical analysis
 
Report drafting and approval
 
Study debrief and review
 
 |

\* Please note that enrolment in the trial to receive product will only occur after all inclusion criteria have been.

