### 2.5. Length of Treatment Time

In total, participants will be required to send the test kits 3 times throughout the total trial time of 6 months.

At the completion of month 6, participants will repeat the baseline measures including a final blood test and a required exit interview.

Clinical interviews will be undertaken by email or phone. The trial will be completed once the last participants complete the exit interview.

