### 2.7. Analysis sets

### 2.7.1. Per protocol set (PPS)

The Per-Protocol Set (PPS) will consist of a subset of participants in the database who complete all 3 tests (baseline, month-3, and month-6 tests).

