### 2.7.2. Intention-To-Treat (ITT)

The Intention-To-Treat (ITT) will consist of a subset of participants in the database who complete at least 2 tests (baseline and month-3 test and/or month-6 test.

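### SAP 2.2 sets a two-test condition for analysis that can be met at month 3, in conflict with the 6-month primary endpoint and the SAP's own post-study timing

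*SAP*

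**What the plan says.** The primary endpoint in SAP 1.1 (Study objectives and endpoints) is "Triglyceride change from baseline over 6-month period". Tests are scheduled at "baseline, month 3 and month 6" (SAP 1.1, Study design).

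SAP 2.2 is the only place that gives a data condition for starting the analysis. The data are to be analysed and reported "when all participants have completed at least 2 tests or discontinued the study (ITT population". SAP 2.7.2 says which tests count: the ITT set holds those who "complete at least 2 tests (baseline and month-3 test and/or month-6 test". Baseline plus month 3 is therefore enough.

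Other statements bear on timing:
- SAP 2.5 puts the final blood test and exit interview at the completion of month 6 and adds: "The trial will be completed once the last participants complete the exit interview".
- Table 2-1 (SAP 2.4, repeated in Protocol 10.1) lists the statistical analysis under the post-study stage, after the end-of-trial blood test and interview. The row just above it is labelled "End-Study Month 3" and has no activity against it.
- SAP 1.1 (Study design) plans comparisons of baseline with both month 3 and month 6.
- SAP 2.7.1 limits the per protocol set to those "who complete all 3 tests (baseline, month-3, and month-6 tests".
- The SAP introduction mentions database lock but ties it to no visit or date.

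**The concern.** The one explicit rule for when the data are ready does not require the visit on which the primary endpoint depends. Someone who follows SAP 2.2 to the letter could open the analysis while some or all participants have only baseline and month-3 results. The ITT definition does not prevent this, because it admits participants without a month-6 test.

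At stake is whether the reported primary result is the 6-month change in triglycerides or a partly 3-month result under that name. The study is open-label and, under SAP 2.1, the sponsor's own personnel run the final analysis. In that setting the date of the data cut should be fixed in advance and not left to a choice between two readings.

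**Working it through.** The plan gives no figure for the timing of the analysis, so there is none to reproduce on this point. The total of 210 in SAP section 3 is used below only as a head count. It does reproduce: 105 per group, two-sided t-test at 0.05, effect size 0.5, power 0.950.

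**1. Earliest time the condition can be met.** Count months from the first participant's start and let the last participant start at R. That participant's month-3 test falls at R + 3, and everyone else has passed month 3 by then. The condition can first be met at R + 3. The last month-6 test falls at R + 6, so the gap is 3 months.

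**2. Share short of month 6 at that time.** A participant who starts at s reaches month 6 at s + 6. That is later than R + 3 when s > R − 3. With uniform starts on 0 to R, the share is min(1, 3/R).

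| Accrual R (assumed) | Short of month 6 | Past month 6 |
|---|---|---|
| up to 3 months | 100% | 0% |
| 4 months | 3/4 = 75% | 25% |
| 6 months | 3/6 = 50% | 50% |
| 9 months | 3/9 = 33% | 67% |
| 12 months | 3/12 = 25% | 75% |

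This ignores discontinuation and assumes kits come back on time. Neither document states R. Table 2-1 starts the one-month pre-study stage once recruitment is complete, which suggests start dates close together. SAP 1.1 (Study design) accepts people by time of application until the quota is full and sends the baseline kit with the first order, which fits rolling starts.

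**3. Is the earliest time the likely one?** The condition covers all participants. Follow-up kits are conditional too: "they will be sent subsequent kits once the confirmed adherence to the supplement". If each of 210 participants independently returns the month-3 kit with probability p, all do so with probability p^210:
- p = 0.95: about 0.00002
- p = 0.99: about 0.12
- p = 0.999: about 0.81

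These return rates are assumptions. A participant who misses month 3 and is not recorded as discontinued holds the condition open until the month-6 test, and indefinitely if that is missed too. If non-returners are recorded as discontinued, the condition moves back towards month 3. Neither document says when someone who fails to return a follow-up kit counts as discontinued, so the date of the data cut depends on an undefined classification.

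**4. The statements side by side.**

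| Place | Timing implied |
|---|---|
| SAP 2.2 with 2.7.2 | from month 3 after the last start |
| Table 2-1, end-of-study row | month 3 |
| Table 2-1, post-study row | after the trial-end interview |
| SAP 2.5 | trial complete after month 6 |
| SAP 1.1, planned comparisons | month-6 data needed |
| SAP 2.7.1 | month-6 test needed |

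The first two rows cannot be squared with the other four.

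**The case against.** The strongest reply is that SAP 2.2 is not a trigger at all. Its heading concerns which data are included, it ends by naming the ITT population, its two-test criterion repeats the definition in 2.7.2, and it never mentions a final analysis. The post-study row of Table 2-1 places the analysis directly, and a month-3 analysis could not deliver the planned month-6 comparison or the per protocol set. Month 6 is probably what the authors intended.

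Much of this stands. It shows a conflict within the SAP, not a clear licence to report early. It does not remove the defect. The sentence attaches a time condition to analysing and reporting, the ITT set is already defined elsewhere, and section 2.5 says when the trial is complete without saying when analysis may start. The per protocol set protects only analyses run on it, whereas SAP 1.1 (Study design) runs its tests on the ITT population.

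Two stronger readings are tempting, and the documents support neither.
- A reader might infer that the final analysis will run at month 3, before any primary data exist. Month 3 is only the earliest possible point, and with accrual longer than 3 months some month-6 data would be in hand. The end-of-study row is weak evidence, since the same table runs to week 24 and month 6.
- A reader might infer that the primary hypothesis would be tested twice, with an inflated false-positive rate. No interim look is planned. Both time points are compared whatever the cut date, so changing the date would not alter that. SAP 1.1 (Study design) also states a Bonferroni threshold of 0.0025, at which two tests carry at most 2 × 0.0025 = 0.5%.

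**Conclusion.** The point holds as an internal contradiction that should be resolved before database lock. Read literally, SAP 2.2 permits analysis up to 3 months before the last month-6 test is due, while the rest of the SAP implies that analysis waits. Between 25% and 100% of participants could be short of month 6 at the earliest trigger, for uniform accrual over 12 months down to 3 months or less. That range rests on assumed accrual and on every participant either returning the month-3 kit or being recorded as discontinued. It is the exposure that the wording allows, not a forecast. That the wording is defective does not depend on these assumptions.

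**What to change.** Replace the timing sentence in SAP 2.2 with wording such as:

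> Database lock and the final analysis take place only when every participant has a month-6 kit result, has passed the month-6 kit-return cut-off, or has discontinued.

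The SAP must specify that cut-off, since neither document defines one now. Keep the two-test criterion only as the definition of the ITT set in SAP 2.7.2. Reconcile the month-3 end-of-study row with the 6-month text in Table 2-1 of the SAP and in the Protocol 10.1 schedule.

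The cost is one SAP sentence, one stated cut-off and one table row in each document. The report may come up to about 3 months later than the literal wording allows, which is still within the planned trial length. If analysis after month 6 was always intended, no time is lost.

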### 2.3. General analysis conventions

**Qualitative data** (e.g., gender, smoking, etc.) will be summarized by means of excel tables, a missing category will be included as applicable. Percentages will be calculated using the number of patients in the relevant population or subgroup as the denominator.

**Quantitative data** (e.g., age, body weight, etc.) will be summarized by appropriate descriptive statistics (i.e., mean, standard deviation, median, minimum, and maximum).

### 2.4. General definitions Investigational Product

### and study treatment

- Investigational Product refers to Iwi/Cholesterol supplement, a commercially available capsule-form herbal (algae) supplement containing Almega®PL, a Nannochloropsis algaederived extract rich in eicosapentaenoic acid (EPA). EPA is a type of omega-3 essential fatty acid known to play a beneficial role in protection against cardiovascular disease. Iwi/Cholesterol is the only source of long chain omega-3 that does not contain the DHA that is present in other omega-3 sources (fish oil, krill oil, other algal oils). Almega®PL was registered at the Food and Drug Administration (FDA) as a New Dietary Ingredient (NDIN) in 2014.
- *Study treatment* = 1000-1100 mg/day investigational product (Almega®PL).

Table 2-1. Treatment plan

| Study Stage                                      | Specific
Timing                          | Activity  |  |  |
|--|---|---|--|--|
| Planning
2 Months                             | N/A   | 
 
Approval of protocol
 
Independent peer-review
 
Logistical arrangements
 
Recruitment
 
   |  |  |
| Pre-Study
1 Month                             | Upon approval and completion of recruitment | Preliminary screening against inclusion and exclusion criteria     Pre-study interview:     Information email and gain informed consent from the participant     Enrolled participants purchase the product and receive the testing kits along with instruction regarding the study requirements. |  |  |
| Study
Week 0-24                               | First test kit will be shipped to imaware   |   |  |  |
| Trial  | Trial Period                                | 
 
Participant takes product as instructed
 
Participant will receive and send the test kits on month 3 and 6
 
   |  |  |
| Months 0-6
(Period begins at
trial week 2) |   | Participant completes end-trial blood test.   |  |  |

### Confidential

4-Mar-2022

|                      | Trial end interview | 
 
Participants exit email or phone interview
to address adherence.
 
   |
|----------------------|---------------------|--|
| End-Study
Month 3 |                     |  |
| Post-Study           | N/A                 | 
 
Data verification and statistical analysis
 
Report drafting and approval
 
Study debrief and review
 
 |

\* Please note that enrolment in the trial to receive product will only occur after all inclusion criteria have been.

### 2.5. Length of Treatment Time

In total, participants will be required to send the test kits 3 times throughout the total trial time of 6 months.

At the completion of month 6, participants will repeat the baseline measures including a final blood test and a required exit interview.

Clinical interviews will be undertaken by email or phone. The trial will be completed once the last participants complete the exit interview.

### 2.6. Baseline

For **non-efficacy assessments, Baseline** is the last available and valid assessment performed or value measured, unless otherwise stated under the related assessment section.

Patients with no data after the testing with the kit but fail to mail back the kit to Imaware or the testing kit gets lost in transit to Imaware before starting supplementation will have no baseline results documented. These participants will have to be discontinued from the study as their baseline results will be compromised once supplementation has begun.

### 2.7. Analysis sets

### 2.7.1. Per protocol set (PPS)

The Per-Protocol Set (PPS) will consist of a subset of participants in the database who complete all 3 tests (baseline, month-3, and month-6 tests).

### 2.7.2. Intention-To-Treat (ITT)

The Intention-To-Treat (ITT) will consist of a subset of participants in the database who complete at least 2 tests (baseline and month-3 test and/or month-6 test.

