As part of the **screening procedure**, participants will complete a short questionnaire to make sure they are new iwi users. Any participant who is already using iwi will not be considered in the study. Any participant that has a serious condition (including but not limited to kidney, neurological, immunological, liver, and gastrointestinal disease, any heart condition, or diabetes) will also be disqualified for the program and directed to their doctor. Any participant attempting conception, pregnant or breastfeeding will also be disqualified. All other participants will be accepted into the limited study based on their time of application until the quota is completed. Participation in this study is purely voluntary and participants can withdraw at any point without prejudice.

Participants will be asked to take the allocated product according to the **dose** prescribed (2 capsules per day containing 1000-1100 mg Almega®PL) and adherence to the protocol will be evaluated with a follow up email. Participants will be asked to maintain their usual level of physical activity and diet for the duration of the study. The dose used in this trial is in agreement with the commercial dose communicated to the FDA and comparable to doses previously used in our clinical trials.

Along with the fist supplement order shipped to the new subscriptions, participants will receive the baseline hearth health test kit from ImawareTM. Participants will be contacted 3 and 6 months after and they will be sent subsequent kits once the confirmed adherence to the supplement. The test kits will monitor blood lipid levels across a supplementation period (baseline, month 3 and month 6) thanks to a finger prick blood drawing system. The age, height, weight, gender, fasting total cholesterol, LDL-cholesterol, HDL-cholesterol, calculated VLDL-cholesterol, triglycerides, as well as hs-CRP inflammatory marker, and glucose and HbA1c as diabetes indicator of each participant will be recorded over the study period. Qualitas Health will receive the aggregated data of the participants only for statistical analyses at their headquarter in Houston and store it in the company share drive with access restricted to those involved in the study. There will be no cost incurred for this analytical assessment to the participant.

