Results for the per protocol (PP) population will be first tested for normality before any other test will be conducted and baseline data was compared again month 3 and month 6 data. Based on the distribution of data, Welch two-sample unequal variance t-tests and Wilcoxon Ranks sum tests were used to compare two-tailed differences between groups. Differences will be considered statistically significant at a p value < 0.05. Intervention effect will also test using an analysis of covariance model (ANCOVA) adjusting for baseline parameters.

10. Study Procedures:

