10.1 Treatment Schedule

Study Stage	Specific Timing	Activity
Planning	N/A	Approval of protocol
2 Months		Independent peer-review

		Logistical arrangements	
		Recruitment	
Pre-Study	Upon approval and	Preliminary screening against inclusion and exclusion criteria	
·		Pre-study interview:	
1 Month	completion	 Information email and gain informed consent from the 	
	of recruitment	participant	
		 Enrolled participants purchase the product and receive the testing kits along with instruction regarding the study requirements. 	
Study	Baseline data collection	First test kit will be shipped to imaware	
Week 0-24	Trial Period	Participant takes product as instructed	
		Participant will receive and send the test kits on month 3 and 6	
		Participant completes end-trial blood test.	
		Participants exit email or phone interview to address adherence.	
Trial			
Months 0-6			
(Period begins at	Trial end interview		
, -			
trial week 2)			
End-Study			
Month 3			
Post-Study	N/A	Data verification and statistical analysis	
		Report drafting and approval	
		Study debrief and review	
*51		receive product will only occur after all inclusion criteria have	

^{*} Please note that enrolment in the trial to receive product will only occur after all inclusion criteria have been met.

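### The SAP's ITT set is an evaluable set, possibly limited to confirmed adherers, and its unpaired month-6 comparison has no rule for missing values

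*SAP*

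**What the plan says.** - **Analysis sets.** Under SAP 2.7.2 the ITT set "will consist of a subset of participants in the database who complete at least 2 tests", spelled out as baseline plus month 3, month 6 or both. SAP 2.7.1 defines the PPS by completion of all three tests. SAP 2.2 uses the ITT label with wording that also mentions discontinued participants. SAP 2.6 discontinues anyone without a baseline result.
- **Kit release.** SAP 1.1 (Study design): "Participants will be contacted 3 and 6 months after and they will be sent subsequent kits once the confirmed adherence to the supplement". Protocol section 9 has the same wording, "they will be sent subsequent kits once the confirmed adherence to the supplement". No adherence threshold is given. The schedule tables (Protocol 10.1, SAP Table 2-1) say "Participant will receive and send the test kits on month 3 and 6". SAP 2.5 and Protocol 10.2 say "participants will be required to send the test kits 3 times throughout the total trial time of 6 months". None of these four places states an adherence condition.
- **Population analysed.** Protocol section 9: "Results for the per protocol (PP) population will be first tested for normality", with PP not defined in that document. SAP 1.1: "Results for the per intended-to-treat (ITT) population will be first tested for normality". The SAP introduction says it follows protocol Amendment version 2; whether the supplied protocol is that version cannot be told.
- **Comparison.** SAP 1.1: "baseline data was compared against month 3 and month 6 data", by Welch or rank-sum two-sample tests, with an ANCOVA as well. The primary endpoint is triglyceride change over six months, and no visit is designated primary.
- **Missing data.** The missing category in SAP 2.3 is for qualitative tables only. Protocol 10.4 and SAP 2.8 keep data collected before consent is withdrawn. Protocol 10.6 and SAP 2.10 allow a GP's decision to lead to removal after out-of-range results, and do not say how such a participant's earlier data are used.

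**The concern.** An ITT label tells the reader that everyone who started is accounted for. Here a participant with a valid baseline who takes the product and returns no follow-up kit is left out. If kits also depend on confirmed adherence, the plan itself creates part of that loss. The SAP asks whether results from a controlled trial carry over to the company's customers; a set of adherers who return kits answers a narrower question.

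The second problem lies in the comparison. A two-sample test does not tie a month-6 value to the same person's baseline. Someone with baseline and month 3 but no month 6 belongs to the ITT set. If that baseline stays in the month-6 contrast, the two means come from different groups of people. Removal after out-of-range results is one described route by which the month-6 group could differ systematically from the baseline group. The ANCOVA uses baseline, but it is not named primary and has no missing-data rule either.

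**Working it through.** **1. The passages together.** Both analysis sets are defined by tests completed, and a test needs a kit. If a follow-up kit needs confirmed adherence, a participant never confirmed has a baseline only and fails both SAP 2.7.1 and 2.7.2. If kits are not gated, that step falls away, but baseline-only participants are still excluded from a set called ITT.

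**2. The SAP's own figure.** SAP section 3 gives effect size 0.5, 1:1 allocation, two independent samples, 95% power and a total of 210. It states no alpha; I take two-sided 0.05 from SAP 1.1. The noncentral-t calculation gives power 0.9501 at 105 per group and 0.9483 at 104, so 2 × 105 = 210 is reproduced. Only the 0.5 is used below, as a yardstick in SD units. How a two-sample calculation fits a single-arm study is a separate matter.

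**3. Illustration of the unpaired contrast.** Neither input is in the documents; both are assumed. Let q be the share of the ITT set with no month-6 test, and δ their baseline mean minus that of the others, in baseline SDs. Suppose nobody changes.

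- Baseline mean of all ITT = stayers' baseline mean + q × δ
- Month-6 mean = stayers' baseline mean
- Apparent change = −q × δ

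| q | δ = 0.5 | share of 0.5 | δ = 1.0 | share of 0.5 |
|---|---|---|---|---|
| 10% | −0.05 | 10% | −0.10 | 20% |
| 20% | −0.10 | 20% | −0.20 | 40% |
| 30% | −0.15 | 30% | −0.30 | 60% |

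With δ = 0 the artefact is zero; with δ negative it is a rise. A simulation (2,000,000 participants per case, within-person correlation 0.6 assumed, no true change) gave the same six contrasts, with a within-participant change of 0.00 among those with month 6.

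**4. What step 3 depends on.** The formula needs stayers to show no change on average. With normal data and correlation 0.6 between all visits:

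- *Loss of the top q on month 3 alone.* δ = 0.6 × φ(z) / [q(1 − q)], where z cuts off the top q and φ is the normal density. For q = 30%: 0.6 × 0.348 / 0.21 = 0.99. So δ = 1.0 at 30% is about the most this route can give. The stayers' within-person change is 0.00.
- *Loss of the top 20% on the average of baseline and month 3.* That average correlates √0.8 = 0.894 with baseline and 0.6 / 0.894 = 0.671 with month 6. Stayers' baseline mean = −0.894 × 0.280 / 0.8 = −0.313; their month-6 mean = −0.671 × 0.280 / 0.8 = −0.235. The unpaired contrast is −0.235, whereas q × δ is 0.313. Completers' own change is −0.235 + 0.313 = +0.078, about +0.08 SD with no true change.

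Simple within-person change in completers is therefore biased too when loss also depends on baseline. In both mechanisms, predicting month 6 from observed baseline and month 3 returned 0.00, because loss then depends only on observed values.

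**The case against.** The gate rests on one garbled sentence. It may mean only a check-in before shipping, and a table that omits a condition need not contradict text that states one. A reader might infer that the trial as written measures confirmed adherers only; the documents do not settle that, because four other places carry no gate.

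Protocol 8.3.3 describes the study as monitoring people who would take the product anyway, and nothing is randomised. The usual argument for ITT is weaker here, and an on-product target may be deliberate. That stands, but it argues for a different label.

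Defining PP in the SAP is ordinary practice, and the PP/ITT difference may be one of versions. With a final blood test at month 6, that visit is the natural reading of the endpoint. These are gaps in explicit wording.

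The rule keeping data collected before consent is withdrawn narrows the missing-data gap. It does not say how a person without a month-6 value enters a month-6 comparison, and it does not cover removal through the GP.

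The illustration concerns the unpaired test, not selection of adherers, and the SAP does not say whether unmatched baselines are kept. A reader might take 60% of the planning effect as an estimate of bias. It is close to an upper bound for one assumed mechanism.

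**Conclusion.** The point holds as a matter of definition and method. The SAP's ITT set is an evaluable set and sits loosely with SAP 2.2. The kit-release sentence and the schedule need reconciling. The two documents name different analysis populations. Repeated measurements on the same people are compared as independent samples, with no rule for missing month-6 triglycerides.

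If all ITT baselines stay in the month-6 contrast, a change in who remains can pass for a change in triglycerides. The 0.05 to 0.30 SD range rests on assumed q and δ and on loss that does not depend on baseline once month 3 is known. The actual bias may be zero or in either direction. The documents do not show that the trial will overstate the effect, or that kits were meant to be withheld from non-adherers. The change is worth making before the analysis, with medium confidence.

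**What to change.** 1. Reconcile Protocol section 9 and SAP 1.1 with Protocol 10.1 and 10.2, SAP Table 2-1 and SAP 2.5, so that month-3 and month-6 kits go to every participant still in the study. Record adherence as data, not as a condition of being measured; the exit interview already asks about it. If an on-product target is intended, say so and do not call it ITT.
2. Name one primary set in both documents: participants with a valid baseline who received product. Reconcile SAP 2.2 with 2.7.2. Relabel the current sets as at least two tests and three-test completers, and keep them as supportive.
3. State that month 6 is the primary time point. Replace the two-sample comparison with a within-participant repeated-measures model that has baseline, month 3 and month 6 as responses. This is valid under missing at random, so add a sensitivity analysis applying a range of shifts to missing month-6 values. Baseline-only participants add no observed change; their contribution rests on the model.
4. State how data collected before removal under Protocol 10.6 and SAP 2.10 enter the analysis, extending the rule in Protocol 10.4 and SAP 2.8. The clinical rule itself is left unchanged.

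**Cost.** Wording in both documents and one model specification. Kits stay within the three per participant already planned: 3 × 200 to 3 × 300 = 600 to 900, of which 400 to 600 are follow-up kits. Against the gated reading, if 10%, 30% or 50% of follow-up contacts went unconfirmed (assumed), 40 to 60, 120 to 180 or 200 to 300 more kits would be sent. Some values will still be missing, and the estimate may be less favourable than in adherers alone.
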